9.6.2.2 Secondary Analyses

These endpoints will also be summarized descriptively by actual treatment group based on Per-protocol Efficacy Analysis Set using observed data.

Sensitivity analyses will be conducted by repeating the models in section 9.6.2.1 using observed data in the FAS according to randomized treatment groups and in the Perprotocol Efficacy Analysis Set according to the actual treatment groups.

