1.3 Schedule of Assessments

Table 1-1. Schedule of Assessments

									We	ek													
	Screen	Baseline	(+ 3 days) (± 3 days)											PK Endpoint Assessments Post Actual Week 28 Dose Date							End of Study (± 3 days) ^a		
Study Visit	≤ 28 days	Week 1/D ay 1	W2/ Day 8	4	6	8	10	12 ^j	14	16	18	20	22	24	26	28 ^b	+1d	+3d	+4d	+7d	+11d	+14d	32
Informed consent	Χ																						
Medical/medication history	Χ																						
Physical examination	Х	Χ																					Х
Height	Χ																						
Weight	Χ	Χ																					Х
Vital signs	Χ	Χ	Χ		Х			Χ		Х		Х				Х						Χ	Х
Adverse events	Xc	Χ	Χ	Х	Х	Χ	Х	Χ	Χ	Х	Χ	Х	Х	Х	Х	Х	Χ	Χ	Х	Χ	Χ	Χ	Х
Concomitant meds	Х	Χ	Х	Х	Х	Х	Х	Χ	Х	Х	Χ	Х	Х	Х	Х	Х	Χ	Х	Х	Χ	Х	Χ	Х
Disease assessments																							
PASI/sPGA/affected BSA	Χ	Χ			Χ			\mathbf{X}^{j}		Х		Χ										Χ	
Laboratory assessments																							
TB Testing ^d	Χ																						
Chest radiography ^e	Χ																						
TB worksheet ^f	Χ																						
Serology (HBsAg, HBcAb, HCV, HIV)	Х																						
Serum pregnancy test	Х																						
Urine pregnancy test		Χ			Х			Χ				Х				Х							Х
Hematology	Χ	Χ			Х			Χ				Х											Х
Chemistry	Х	Χ			Х			Χ				Х											Х
Urinalysis	Х	Χ																					Х
Pharmacokinetic sample ^h		Х			Х			Χ		Х		Χ				Χg	Χ	Χ	Χ	Χ	Χ	Χ	Х
Antidrug antibody sample ^h		Χ			Х			Χ		Х		Χ				Х						Χ	Х
Investigational product																							
Randomization								Χ															
IP administration ⁱ		Χ	Χ	Χ	Х	Х	Х	Χ	Χ	Х	Χ	Х	Х	Χ	Х	Χ							

Clinical Study Protocol: 20200497

Final 1.0 Date: 03 Jun 2021 Page **18** of **87**

BSA = body surface area; CT = computed tomography; HBcAb = hepatitis B core antibody; HBsAg = hepatitis B surface antigen; HCV = hepatitis C virus; HIV = human immunodeficiency virus; IP = investigational product; MRI = magnetic resonance imaging; PASI = Psoriasis Area and Severity Index; PK = pharmacokinetics; PPD = purified protein derivative; sPGA = static Physician's Global Assessment; TB = tuberculosis.

- ^a Subjects terminating early from the study should complete all procedures scheduled for EOS Visit (ie, week 32) within 28 days after withdrawal/discontinuation if possible.
- b Week 28 visit will have a window of ± 3 days.
- ^c Report serious adverse events that occur after signing informed consent form. Nonserious adverse events are reported as medical history prior to enrollment.

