A subject may be discontinued from the study at any time at the discretion of the investigator for safety, behavioral, or administrative reasons, including, but not limited to:

Requirement for alternative therapy per the investigator's determination

Clinical Study Protocol: 20200497

Final 1.0 Date: 03 Jun 2021 Page **42** of **87**

 The subject develops a malignancy (exception: subjects may be allowed to continue if they develop no more than 2 non-melanoma skin cancers during the study)

- Adverse events or serious adverse events
- Any laboratory abnormalities that in the judgment of the investigator, taking into consideration the subject's overall status, prevents the subject from continuing participation in the study
- Any other reason relating to the subject's safety or integrity of the study data
- Noncompliance with study procedures
- Withdrawal of consent from the study
- Lost to follow-up
- Decision by sponsor/investigator
- Death

Refer to the Schedule of Assessments (Table 1-1) for data to be collected at the time of study discontinuation and evaluations that need to be completed.

If a subject withdraws or is discontinued from the study, the CRA will be informed immediately.

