9.5.2.2 Secondary Efficacy Endpoints

The analysis of the secondary efficacy endpoints will be based on the Per Protocol Efficacy Analysis Set according to the actual treatment groups (switching group versus continued-use group). The point estimate and 90% CI of the mean difference in PASI percent improvement from day 1 at week 30 will be estimated from an ANCOVA model adjusting for the baseline PASI value and the stratification factors. The point estimate and 90% CI of the risk differences in PASI 75, PASI 90, and PASI 100 response rates at week 30 will be estimated from a generalized linear model with an identity link adjusting for the stratification factors.

Missing data will be imputed by last observation carry forward method for PASI percent improvement from day 1 at week 30 and by non-responder imputation for PASI 75, PASI 90, and PASI 100 response rates at week 30. In addition, the PASI percent improvement from day 1 at week 30 and the PASI 75, PASI 90, and PASI 100 response rates at week 30 will be summarized descriptively by treatment group.

Clinical Study Protocol: 20200497

Final 1.0 Date: 03 Jun 2021 Page **63** of **87**

A sensitivity analysis will be conducted using observed data based on the Full Analysis Set according to randomized treatment groups.

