Developing antibody incidence during the Post-randomization Period is defined as the number of subjects in the Safety Analysis Set (SAS) who have a positive result post randomization and have never tested positive (i.e., negative or no results) prior to the first dose of post-randomization IP divided by the number of subjects in the SAS who have at least a result post randomization.

End of Study (EOS) Date

The EOS date is the date recorded on the End of Study page of the CRF.

First Dose Date

It is defined as the date the subject received the first dose of IP.

First Post-randomization Dose Date

It is defined as the date the subject received the first post-randomization dose of IP.

Last Dose Date

It is defined as the date the subject received the last dose of IP.

Last Observation Carried Forward (LOCF)

Protocol Number: 20200497

Date: 10FEB2023 Page 14 of 36

A method of imputation where missing post-baseline data will be imputed by carrying forward the last non-missing post-baseline value for that endpoint. Baseline values will not be carried forward.

Neutralizing ADA Negative Subgroup

Defined as subjects in the subset of Safety Analysis Set (SAS) who have never tested positive (i.e. tested negative or no results) prior to the first dose of post-randomization IP, have at least one neutralizing ADA result post-randomization, and all available post-randomization neutralizing ADA results are negative.

Non Responder Imputation (NRI)

A method of imputation where a subject with missing post-baseline binary response data will be imputed as a non-responder, regardless of the reasons for missing data.

Study Analysis Visit

If more than one actual visit (including the unscheduled visits) falls within the same defined window, the visit closest to the target day with non-missing data will be considered for analysis. If two actual visit dates are at the same distance from the target day, the later visit with non-missing data will be considered for analysis.

For Efficacy, Vital, Safety Lab & PK

					Endpoint	
Study Analysis Visit	Target Day	Study Day	Interval (days)	Efficacy	Vital & Safety Labª	PK
Baseline ^b	1	≤1	NA	Х	Х	Х
Week 2	8	2-21	20		X	
Week 6	36	22-56	35	Χ	X	Χ
Week 12 ^b	78	57-91	35	Χ	X	Χ
Week 16	106	92-119	28	Χ	X	Χ
Week 20	134	120-161	42	Χ	X	Χ
Week 28	190	162-196	35		X	Χ
Week 30	14 days post week 28 dose	197-210	14	Х	Х	
Week 32	218	≥211	NA		Χ	

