6.5 Per-protocol Efficacy Analyses Set

The Per-protocol Efficacy Analysis Set consists of all subjects who are randomized and receive all assigned doses post-randomization and who have not experienced an important protocol deviation that may affect the evaluation of the efficacy endpoints. This analysis set will be used for primary analysis of the secondary efficacy endpoints and will be analyzed according to actual treatment received.

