9.6.2 Analyses of Secondary Efficacy Endpoint(s)

9.6.2.1 Primary Analysis

The primary analysis will be performed based on the Per-protocol Efficacy Analysis Set according to the actual treatment groups with missing PASI score at Week 30 visit imputed by LOCF and missing PASI 75, PASI 90 and PASI 100 response at week 30 imputed by NRI. Confidence interval for response rates will be calculated by the Clopper-Pearson method.

The point estimate and 90% CI of the mean difference in PASI percent improvement from baseline at Week 30 will be estimated from an ANCOVA model adjusting for the baseline PASI value and the stratification factors.

Protocol Number: 20200497

Date: 10FEB2023 Page 30 of 36

The point estimate and 90% CI of the risk difference in PASI 75, PASI 90, and PASI 100 response rates at Week 30 will be estimated from a generalized linear model with an identity link adjusting for the stratification factors.

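### Subjects who leave before the week 28 dose normally enter no week-30 efficacy model, because non-responder imputation is never applied to the Full Analysis Set

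*SAP*

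**What the plan says.** **Main efficacy models.** SAP 9.6.2.1 analyses week-30 PASI in the Per-protocol Efficacy set. The PASI score is imputed by last observation carried forward (LOCF), with "missing PASI 75, PASI 90 and PASI 100 response at week 30 imputed by NRI". Under SAP 6.5 that set "consists of all subjects who are randomized and receive all assigned doses post-randomization and who have not experienced an important protocol deviation" that could affect the efficacy evaluation. Protocol Table 9-1 has the same requirement. Post-randomization dosing runs from week 12 to week 28.

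**Full Analysis Set (FAS) models.** SAP 9.6.2.2 repeats the models "using observed data in the FAS according to randomized treatment groups", and again on observed data in the per-protocol set. Protocol 9.5.2.2 agrees: "A sensitivity analysis will be conducted using observed data based on the Full Analysis Set according to randomized treatment groups".

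**Other week-30 models.** SAP 9.6.3 places the sPGA 0/1 model (non-responder imputation, NRI) and the BSA model (LOCF) in the per-protocol set only.

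**Imputation rule.** Under NRI in SAP 5.1, a subject with a missing binary response "will be imputed as a non-responder, regardless of the reasons for missing data".

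**Assessments and leavers.** After randomization, Table 1-1 of the protocol schedules PASI, sPGA and BSA at weeks 16 and 20 and 14 days after the week 28 dose. None is scheduled at week 32. Footnote a says: "Subjects terminating early from the study should complete all procedures scheduled for EOS Visit". Protocol 7.2 lists among the reasons for discontinuing a subject: "Requirement for alternative therapy per the investigator's determination".

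**The concern.** The imputation and the set of all randomized subjects never meet. NRI is there to count a subject with no outcome as a failure, but the set it is confined to has already excluded almost everyone who left. The set that keeps the leavers uses only observed values, and leavers normally have none.

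Protocol 2.1 and 4.2 state the aim as showing that switching carries no greater risk of reduced efficacy. Leaving because the drug has stopped working is one of the ways such a loss would appear. Under the plan, an arm imbalance in such departures would show in the disposition and set-exclusion tables (SAP 9.2) but in no response rate, risk difference or confidence interval.

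**Working it through.** **Step 1. Trace a randomized subject who leaves the study before the week 28 dose.**

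| Planned week-30 model | Set | Missing data | Is the subject in it? |
|---|---|---|---|
| PASI % improvement, PASI 75/90/100 (SAP 9.6.2.1) | Per-protocol Efficacy | LOCF / NRI | No: doses missing |
| Same, sensitivity (9.6.2.2) | FAS | Observed only | Normally no: no week-30 PASI |
| Same, sensitivity (9.6.2.2) | Per-protocol Efficacy | Observed only | No: doses missing |
| sPGA 0/1, BSA (9.6.3) | Per-protocol Efficacy | NRI / LOCF | No: doses missing |

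The end-of-study visit does not supply the value, because it has no scheduled PASI and the SAP 5.1 window table lists no week-32 efficacy visit. Protocol 7.2 does not let a subject who has left rejoin.

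There are three exceptions:

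- A subject who leaves between the week 28 dose and week 30 can stay in the per-protocol set and be imputed.
- A subject who stops drug but stays in the study (Protocol 7.1) can have a week-30 PASI and enter the FAS run.
- An unscheduled PASI on study days 197-210 would count, since under SAP 5.1 "the visit closest to the target day with non-missing data will be considered for analysis".

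**Step 2. How many subjects could be affected.** The plan gives no sample size or power for efficacy, so there is no efficacy figure to reproduce. SAP 3.2 assumes 342 randomized (171 per arm) and 15% loss: 342 × 0.15 = 51.3. On that assumption about 51 is an upper bound on leavers, because the 15% also counts subjects who reach week 28 without an evaluable PK profile.

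**Step 3. Effect on the risk difference (illustration).** The response and leaving rates are assumptions; the documents give none. All leavers go before the week 28 dose, all stayers are observed, and stayers respond at the same rate *r* in both arms.

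- Observed-data FAS difference = *r* − *r* = 0.
- FAS-NRI rate per arm = *r* × (1 − leaving rate), so the difference is −*r* × (leaving rate, switching − leaving rate, continued use).
- 90% CI: unadjusted Wald, z = 1.645.

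With *r* = 0.85:

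| Leaving, switching vs continued | Observed FAS | FAS with NRI |
|---|---|---|
| 10% vs 10% | 0 | 0 |
| 10% vs 5% | 0 (−6.6 to +6.6) | 0.7650 − 0.8075 = −4.3 points (−11.5 to +3.0) |
| 15% vs 5% | 0 | 0.7225 − 0.8075 = −8.5 points (−16.0 to −1.0) |

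For 10% vs 5%:

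- NRI: SE = √[(0.765 × 0.235 + 0.8075 × 0.1925)/171] = 0.0443, half-width 0.073.
- Observed: SE = √[0.85 × 0.15 × (1/153.9 + 1/162.45)] = 0.0402, half-width 0.066.

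For 15% vs 5%, NRI: SE = √[(0.7225 × 0.2775 + 0.8075 × 0.1925)/171] = 0.0456, half-width 0.075.

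With *r* from 0.70 to 0.90, the NRI difference is −3.5 to −4.5 points at 10% vs 5%, and −7.0 to −9.0 at 15% vs 5%.

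By number of leavers at *r* = 0.85:

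- 12 vs 6: −0.85 × 6/171 = −3.0 points
- 22 vs 11: −0.85 × 11/171 = −5.5 points
- 34 vs 17: −0.85 × 17/171 = −8.5 points
- 26 vs 25: −0.85 × 1/171 = −0.5 points

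**The case against.** **Efficacy carries no formal test.** Only AUCtau and Cmax have hypotheses and margins, and Protocol 2.1 calls the efficacy assessment descriptive. This stands. It limits the point to a gap in a supportive analysis.

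**NRI is not always the stricter check in a similarity study.** This also stands. With 75% vs 85% response among stayers and 15% leaving each arm, NRI shrinks a true −10.0 points to 0.85 × (−10.0) = −8.5. It is a reason to show both runs rather than replace one with the other.

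**The imbalance is assumed.** The plan gives no loss by arm, only week-12 PASI 50 responders are randomized, and the study is blinded. The one illustrated interval that excludes zero needs a three-fold difference in leaving. All true, but the added run shows close to nothing when loss is balanced and matters when it is not, which cannot be known in advance.

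**Worsening psoriasis could surface as an adverse event leading to discontinuation** (Protocol 8.3.1.1.1; SAP 9.7.1, item h). That is a further route by which the signal might be seen, but it is not a response estimate.

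**The all-doses condition might cover only doses due before withdrawal.** SAP section 10 argues against this. It describes the former PK Parameter set, which had the same condition, as possibly too restrictive and relaxes it there. The efficacy set keeps it.

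**The remedy is partial.** Leavers would still enter no model for PASI percent improvement or BSA, and sPGA is not a secondary endpoint. Both remarks are fair. Neither weakens the case for PASI 75, 90 and 100.

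**Conclusion.** The concern holds. Apart from the three exceptions, a subject who leaves before the week 28 dose contributes to no planned week-30 efficacy model. In practice NRI reaches only subjects who took every dose through week 28 and then lack a PASI about 14 days later.

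The size depends on how unevenly the arms lose subjects. Under the assumed rates, the risk difference that the plan would report as 0 becomes about −3.5 to −9.0 points when leaving differs by 5 to 10 percentage points. It stays at 0 when leaving is equal. The tracing rests on the documents alone; the magnitudes rest on the assumed response and leaving rates.

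The similarity decision on AUCtau and Cmax is untouched. This should be corrected as a matter of good supportive analysis, but it is not a flaw in the primary inference.

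**What to change.** - **SAP 9.6.2.2:** add a sensitivity analysis of PASI 75, PASI 90 and PASI 100 at week 30 in the FAS by randomized group, using the 9.6.2.1 model and NRI as defined in SAP 5.1. Report it beside the observed-data FAS run.
- **SAP 9.6.3:** add the same pair (FAS observed, FAS with NRI) for sPGA 0/1 at week 30. This has lower priority, since sPGA is not a secondary endpoint.
- **PASI percent improvement:** leave it on observed data in the FAS, and say that early leavers are not represented there. Do not add LOCF in the FAS. The last scheduled PASI before week 30 is at week 20, and Protocol section 8 puts dosing after all other procedures. That value therefore precedes the first dose of the final switch. The planned per-protocol LOCF has the same weakness for the few subjects it reaches.

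The cost is a few more model runs on data already collected, under a rule already defined. The drawback is that administrative drop-outs count as failures, which lowers response rates and can dilute a true difference, so both runs should be shown. If treatment allocation has already been released, label the added runs post hoc.

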9.6.3 Analyses of Other Efficacy Endpoint(s)

The analyses of the other efficacy endpoints in this section will be based on the Perprotocol Efficacy Analysis Set by actual treatment group.

The PASI percent improvement from day 1 at weeks 6, 12, 16 and 20 and the PASI 75, PASI 90 and PASI 100 response rates at weeks 6, 12,16 and 20 will be summarized descriptively by treatment group based on observed data.

BSA absolute values and changes from baseline will be summarized descriptively by visit (at weeks 6, 12, 16, 20 and 30) and treatment group using observed data. In addition, the point estimate and 90% CI of the mean difference in the change from baseline for BSA at Week 30 between the two groups will be estimated from an ANCOVA model adjusting for the baseline BSA value and the stratification factors with missing values imputed by LOCF.

sPGA scores will be summarized descriptively by visit (at weeks 6, 12, 16, 20 and 30) and treatment group. sPGA response (0/1) will also be summarized descriptively by visit and treatment group using observed data. The sPGA response (0/1) at Week 30 will be analyzed by a generalized linear model adjusting for the stratification factors with missing values imputed by NRI. Confidence interval for response rate will be calculated by the Clopper-Pearson method.

9.7 Safety Analyses

Safety analyses of the safety endpoints during the Post Randomization Period and the Lead-in Period will be performed based on the SAS and LTS, respectively, according to actual treatment received.

Protocol Number: 20200497

Date: 10FEB2023 Page 31 of 36

9.7.1 Adverse Events

For summary of AEs, the following summaries, (a) through (n), will be provided for the Post Randomization Period. In addition, summaries (a), (e), (f), (l) without risk difference, (m) and (n) will be provided for the Lead-in Period.

- (a) overall summary of TEAEs,
- (b) TEAEs by PT,
- (c) TEAEs by SOC and PT,
- (d) TEAEs by SOC, PT, and maximum severity grade,
- (e) treatment-emergent SAEs by PT,
- (f) treatment-emergent SAEs by SOC and PT,
- (g) grade 3 or higher TEAEs by PT,
- (h) TEAEs leading to discontinuation from IP/study by PT,
- (i) TEAEs leading to dose delayed of IP by PT,
- (j) fatal TEAEs by PT,
- (k) treatment-emergent EOIs by PT,
- (I) overall summary of treatment-emergent EOIs with risk difference,
- (m) treatment-emergent COVID-19 AEs by PT,
- (n) treatment-emergent SAEs occurring on or after the presumed start date of COVID-19 infection by PT

Counting of AEs will be by subject, and subjects will be counted only once within each SOC or PT by study period. For tables categorized by severity, subjects with multiple event PTs within a particular SOC will be counted under the category of their most severe event PT within that SOC.

AEs tabulated by preferred term will be presented in descending order of frequency of the switching group for the Post-randomization Period or the Humira group for the Leadin Period.

The risk difference and 90% CI of each treatment-emergent EOI will be calculated using Wald asymptotic confidence limits or exact confidence limits if the number of subjects for any treatment is less than 25.

A listing of treatment-emergent SAEs will be provided for the Post-randomization Period and the Lead-in Period separately.

Protocol Number: 20200497

Date: 10FEB2023 Page 32 of 36

All serious TEAEs occurring on or after the presumed start date of COVID-19 infection will be listed.

COVID-19 AEs will be flagged based on COVID-19 standardized query (SMQ) of the current MedDRA version at the time of the final analysis.

